10.4.2. Efficacy analyses

The analysis of the efficacy endpoints will be performed on the EPP and repeated on the SAF. The analysis of efficacy will be based on RECIST 1.1.

• Overall Response Rate (ORR)

Overall response rate (ORR) is defined as the proportion of patients whose best overall response is either CR or PR according to RECIST version 1.1. Proportions of patients with a best overall response of CR or PR will be presented along with exact 95% confidence intervals. Patients with best overall response ‘unknown’ will be summarized by reason for having unknown status. Phase II part 2: ORR will be compared between the 2 treatment arms using a (two-sided) 95% CI for the difference in proportion of patients whose best overall response is either CR or PR, stratified by indication using Cochran-Mantel-Haenszel Chi-Square test.

• Progression Free Survival (PFS)

Phase Ib and phase II part 1: PFS (in months) is defined as the time from the date of first study treatment administration to the date of first documented tumor progression or death due to any

cause, whichever occurs first. PFS will be censored if no progression or death is observed at the cut-off date for analysis, or at the date when a further antineoplastic therapy is started. The censoring date will be the date of the last evaluable tumor assessment before the cut-off date or start of further antineoplastic therapy.

Phase II part 2: PFS (in months) is defined as the time from the date of randomization to the date of first documented tumor progression or death due to any cause, whichever occurs first. PFS will be censored if no progression or death is observed at the cut-off date for analysis, or at the date when a further antineoplastic therapy is started. The censoring date will be the date of the last evaluable tumor assessment before the cut-off date or start of further antineoplastic therapy. The primary analysis will be a comparison of PFS between the 2 treatment arms using an unstratified log rank test at the one-sided 5% level in the FAS. A stratified log rank test stratified by indication will be also performed as supportive analysis. [REDACTED]

[REDACTED] HR (together with associated 95% CI) resulting from the stratified and unstratified Cox model will also be presented.

PFS will be presented descriptively using Kaplan-Meier curves. Summary statistics from the Kaplan-Meier distributions will be determined.

- **Duration of Overall Response (in case of CR or PR)**

Duration of overall response in months (DoR) applies only to patients whose best overall response is CR or PR. The start date is the date of first documented response (CR or PR) and the end date is the date of event defined as first documented disease progression or death due to underlying cancer.

DoR will be censored if progression or death due to underlying cancer is not observed at the cut-off date for the analysis or start of further antineoplastic therapy. The censoring date will be the date of the last evaluable tumor assessment. Kaplan-Meier curves of DoR will be constructed. Summary statistics from the Kaplan-Meier distributions will be determined.

- **Disease Control Rate (DCR)**

Disease control rate (DCR) is defined as the proportion of patients whose best overall response is either CR, PR, or stable disease (SD).

- **Overall Survival (OS)**

Phase Ib and phase II part 1: OS is defined as the time from the date of first study treatment administration to the date of death due to any cause. If a patient is not known to have died, survival will be censored at the date of last contact.

Phase II part 2: OS is defined as the time from the date of randomization to the date of death due to any cause. If a patient is not known to have died, survival will be censored at the date of last contact. OS will be presented descriptively using Kaplan-Meier curves. Summary statistics from the Kaplan-Meier distributions will be determined. OS will be compared between the 2 treatment arms using an unstratified log rank test and log-rank stratified by indication at the one-sided 5% level in the FAS. [REDACTED]

[REDACTED] HR (together with associated 95% CI) resulting from the stratified and unstratified Cox model will also be presented.

- **Phase II part 2: Percentage of patients with liver metastases at baseline who have disease progression at D43**

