8 ASSESSMENT OF EFFICACY

- Assessment of efficacy according to RECIST VERSION 1.1

The assessment of efficacy is based on Response Evaluation Criteria in Solid Tumors (RECIST) version 1.1 (Eisenhauer E.A. *et al.*, 2009).

For efficacy evaluation, patients must have at least one measurable lesion by CT/MRI scan (minimum size not less than 10 mm) at baseline and a post-baseline evaluable CT-scan at week 6 after start of study treatment with a best overall response assessment different from 'Unknown' according to RECIST evaluation criteria. However, if a patient progressed or died due to underlying cancer before scheduled scan 6 weeks after study treatment start could be performed, the patient will still be included in the evaluable population.

Tumor assessment will be performed LOCALLY according to investigator's assessment every 6 weeks from the start of study treatment until disease progression or for a period of 9 months after start of study treatment, whichever occurs first. Beyond 9 months after start of study treatment, the evaluations will be performed every 12 weeks until disease progression. The same schedule of tumor evaluation will be applied for patients who stopped the study treatment for any reason other than progressive disease.

For all patients, tumor response assessment will be performed by preferably CT (or MRI) of the head and neck, chest, abdomen and all other known sites of disease (e.g. pelvis, if applicable) and other established assessments of tumor burden if CT/MRI imaging is insufficient for the individual patient. In case of bone pain, an adequate radiological and/or isotopical exploration is to be performed to research metastases. All the scans performed at baseline and other imaging performed as clinically required (other supportive imaging) need to be repeated at subsequent visits.

Per RECIST, the imaging method used at baseline should be matched at all subsequent assessments, but, for a number of reasons such as site error (e.g. switch from MRI to CT) or renal dysfunction (making contrast a risk), this will not always be done. A strict implementation of RECIST would mean that any change in imaging method compared to one used at baseline should lead to unknown overall response at given assessment. However, a change in the use of contrast does not necessarily represent a change in precision since for many tumor types, the assessment can be done despite the fact that contrast has changed.

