Phase II part 1: Evaluable patients' population for tumor response (evaluable per protocol population, EPP): consists of all included patients who were dosed with both IMPs (TG4001 + avelumab) and have at least one baseline and one post-baseline evaluable CT-scan at week 6 after start of study treatment with a best overall response assessment different from 'Unknown' according to RECIST 1.1 evaluation criteria. However, if a patient progressed or died due to underlying cancer before scheduled scan 6 weeks after study treatment start could be performed, the patient will still be included in the evaluable population. Any patient who has a major inclusion/exclusion violation, major dosing violation, or major protocol conduct violation will be excluded from the EPP. Major dosing violation is considered when minimum exposure is not met defined as at least 6 TG4001 injections and 3 avelumab administrations except if patient has progressed or died due to underlying disease before or at the first evaluation. Due to potential abscopal effect when associating radiotherapy and immunotherapy, patients receiving palliative radiotherapy will be analyzed separately. Whatever the reason for withdrawal, except for disease progression and death due to underlying cancer before scheduled scan 6 weeks after study treatment start could be performed, patients considered as non-evaluable for tumor response will be replaced.

Phase II part 2: Full Set Analysis (FAS) will be the primary set for efficacy analyses. It consists of all randomized patients who were administered at least one dose of IMP(s) according to the treatment allocated at randomization.

Evaluable patients' population per protocol (evaluable per protocol population, EPP): consists of all patients from the FAS without any major inclusion/exclusion violation, major dosing violation as defined for phase II part 1, or major protocol conduct violation who were dosed with IMP(s) according to the treatment allocated at randomization and have at least one baseline and one post-baseline evaluable CT-scan at week 6 after start of study treatment with a best overall response assessment different from 'Unknown' according to RECIST 1.1 evaluation criteria.

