10.3. Study endpoints

10.3.1. Primary endpoint

Phase Ib: Dose limiting toxicities defined as follows:

- Grade ≥ 3 drug related adverse event. However, fatigue, nausea/vomiting adequately treated with anti-emetics, endocrinopathies adequately controlled with one physiologic hormone replacement, skin toxicity and single laboratory values out of normal range without any clinical correlate, asymptomatic grade ≥ 3 lipase or amylase elevation, tumor flare defined as local pain, irritation, or rash localized at sites of known or suspected tumor or a transient Grade 3 infusion adverse event are excluded
- Liver function test abnormality:
 - o AST or ALT $> 5 \times$ ULN
 - o Total bilirubin $> 3 \times$ ULN
 - o Concurrent AST or ALT $> 3 \times$ ULN and total bilirubin $> 2 \times$ ULN
- Drug related adverse event requiring treatment interruption for more than 2 weeks

The RP2D will be defined as the dose at which less than 33% of the patients (0 or 1 patient among 6 evaluable patients) experience a DLT.

Dose limiting toxicities will be assessed during the first 4 weeks of the combination and will be graded according to NCI CTCAE version 4.03.

To be evaluable for the primary objective of the phase Ib of the study, patients must complete the first 4 weeks of the combination or discontinue before the end of the 4 weeks for a DLT. Patients must receive at least one dose of both IMPs (TG4001 + avelumab) and have at least one valid post-baseline safety assessment. The statement that a patient had no AE, on the Adverse Events eCRF page, constitutes a valid safety assessment. The occurrence of death also constitutes a valid safety assessment. Patients who are not evaluable for phase Ib safety analysis or are withdrawn for other reasons than toxicity, will be replaced.

The DLT population will be the primary population for analyses. These analyses will be repeated on the SAF.

Phase II part 1: The primary endpoint of the phase II part 1 is the Overall Response Rate (ORR by RECIST 1.1 criteria).

The EPP will be the primary population for efficacy analyses in the phase II part 1. These analyses will be repeated on the SAF.

The best response will be recorded from the first study drug administration until documented disease progression. A PR or CR must be confirmed at a subsequent evaluation at least 4 weeks apart.

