Phase II part 2: The primary endpoint of phase II part 2 is PFS by RECIST 1.1 criteria. The FAS will be the primary population for efficacy analyses in the phase II part 2. These analyses will be repeated on the EPP.

Progression Free Survival (PFS) is defined as the time from the date of randomization to the date of first documented tumor progression or death due to any cause, whichever occurs first. If a patient has not had a PFS event at the cut-off date for analysis or at the date when a further antineoplastic therapy (other than those planned as study treatment in the protocol) is started, PFS will be censored at the date of last evaluable tumor assessment before the cut-off or start of further antineoplastic therapy.

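### Section 10.4.2 makes the per-protocol set the main set for the part 2 response-rate comparison, against the FAS rule in Sections 10.1 and 10.3.1

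*Combined protocol and SAP*

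**What the plan says.** Three places set the analysis population for efficacy.

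- **Section 10.1** (and the synopsis, Statistical Methods) says that for part 2 the FAS "will be the primary set for efficacy analyses". Its definition: "It consists of all randomized patients who were administered at least one dose of IMP(s) according to the treatment allocated at randomization".
- **Section 10.3.1** gives a rule for each part. Part 1: "The EPP will be the primary population for efficacy analyses in the phase II part 1", with a repeat on the SAF. Part 2: "The FAS will be the primary population for efficacy analyses in the phase II part 2", and then "These analyses will be repeated on the EPP".
- **Section 10.4.2** opens with one sentence for every endpoint and names no part: "The analysis of the efficacy endpoints will be performed on the EPP and repeated on the SAF". Further down, the part 2 log-rank tests for PFS and OS are placed in the FAS. The part 2 ORR comparison (95% CI for the difference, stratified by indication with Cochran-Mantel-Haenszel) names no set. Neither do DCR and DoR.

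Section 8 adds a condition for efficacy evaluation, again without naming a part: a measurable baseline lesion and "a post-baseline evaluable CT-scan at week 6 after start of study treatment with a best overall response assessment different from 'Unknown".

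The part 2 EPP in Section 10.1 takes FAS patients and removes those with major violations of eligibility, dosing or conduct, and those without an evaluable week-6 scan. A major dosing violation is carried over from part 1: fewer than 6 TG4001 injections or fewer than 3 avelumab administrations, unless the patient progressed or died of the disease before or at the first evaluation.

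**The concern.** For part 2, the main set and the repeat set both differ between 10.4.2 and 10.3.1. Because 10.4.2 names the FAS for two endpoints only, a programmer following that section would put the rest on the EPP. ORR is a listed part 2 secondary endpoint and has a planned between-arm comparison.

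The EPP is formed by what happens after randomisation: how many doses were given and whether a scan was evaluable. Part 2 is open label and only one arm receives TG4001, so these exclusions need not be balanced. Leaving the main set unsettled also allows it to be chosen once results are known.

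**Working it through.** **1. The rules side by side, part 2**

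| Endpoint | Main / repeat by 10.1 and 10.3.1 | Main / repeat by 10.4.2 | Conflict? |
|---|---|---|---|
| PFS (primary) | FAS / EPP | FAS named for the test | Main set agrees |
| OS | FAS / EPP | FAS named for the test | Main set agrees |
| ORR, between-arm | FAS / EPP | No set named, so EPP / SAF | Yes |
| DCR, rate per arm | FAS / EPP | No set named, so EPP / SAF | Yes, in the denominator |
| DoR | FAS / EPP | No set named, so EPP / SAF | Yes, but responders only |

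**2. Nothing in the sample size depends on this.** Section 10.2 states 76 events from medians of 4.5 and 2.0 months, one-sided 5% and 95% power. With HR = 2.0/4.5 = 0.444, Freedman's formula gives (1.645 + 1.645)² × (1.444/0.556)² ≈ 73.2, so 74 events, within 2 of the stated 76. No response rate enters.

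**3. Who the EPP removes in the combination arm.** Section 7.3 schedules TG4001 on Days 1, 8, 15, 22, 29 and 36 (6 injections) and avelumab on Days 8, 22 and 36 (3 infusions). The minimum exposure is thus everything due by Day 36. A patient who stops for toxicity in week 3 has had at most 3 injections (Days 1, 8, 15) and 1 infusion (Day 8). That patient is outside the EPP even if the week-6 scan is done, and inside the FAS denominator.

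**4. Who the EPP keeps in the avelumab-alone arm.** These patients receive 0 TG4001 injections, so none can reach 6. Read literally, only those covered by the exemption remain, that is, patients who progressed or died of the disease by the first evaluation. Assuming exponential PFS with the planned 2.0-month median, week 6 is 42/30.4375 = 1.38 months, and 1 − 0.5^(1.38/2.0) = 0.380, or about 15 of 40. Their ORR and DCR would be near zero by construction.

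**5. Sensitivity of the ORR difference.** All responder and exclusion counts here are assumed, and the TG4001 minimum is taken as waived in the avelumab-alone arm. There are 40 patients per arm (Section 10.2). Responders are 14/40 v 4/40, close to the 34.8% in patients without liver metastases (Section 1.3.8) and the 10% for avelumab alone in anal carcinoma (Section 1.3.7).

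| Removed (combination, control) | ORR | Difference, points |
|---|---|---|
| none (FAS) | 14/40 = 35.0% v 4/40 = 10.0% | 25.0 |
| 5, 5 non-responders | 14/35 = 40.0% v 4/35 = 11.4% | 28.6 |
| 5, 0 non-responders | 40.0% v 10.0% | 30.0 |
| 0, 5 non-responders | 35.0% v 11.4% | 23.6 |
| 8, 0 non-responders | 14/32 = 43.8% v 10.0% | 33.8 |
| 0, 8 non-responders | 35.0% v 4/32 = 12.5% | 22.5 |
| 5, 0, of whom 2 responded | 12/35 = 34.3% v 10.0% | 24.3 |

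The difference moves either way, depending on which arm loses patients and whether under-dosed responders are among them.

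**The case against.** The part 2 FAS rule appears three times, each time naming part 2, and Section 10.3.1 applies it to efficacy analyses generally, not only to PFS. The opening sentence of 10.4.2 matches the part 1 rule and is probably carried-over text. On ordinary reading the specific statements would prevail. That is the likely intent, but the document states no order of precedence, and 10.4.2 is the section that specifies the analyses.

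Early stoppers are not lost on either reading. The SAF holds everyone who received any study treatment and in part 2 is close to the FAS. This stands: what is in dispute is which table is the main result. It also removes any clash with the plan in 10.4.2 to summarise unknown best responses by reason, since those patients are in the SAF repeat.

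Section 8 can fairly be read as describing the evaluable population, because its next sentence speaks of inclusion in that population. Scans also continue after treatment stops for reasons other than progression (Section 7.7), so stopping early does not by itself mean a missing week-6 scan. Both points stand. The exposure rule still excludes such patients in the combination arm.

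Sections 10.2 and 10.6 leave the adaptive method and the deviations that determine the EPP to a statistical analysis plan. Those passages do not say which set is main for ORR. If a separate plan settles it, the protocol text should still agree.

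**Conclusion.** The inconsistency is real and confined to part 2 secondary endpoints: the main set for the between-arm ORR comparison and the denominator of each arm's DCR. Following 10.4.2 would rest a randomised comparison on a set selected after randomisation, one whose exposure minimum the avelumab-alone arm cannot meet.

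Four stronger readings are tempting, and the documents do not support them:

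- **The primary analysis is on the wrong set.** It is not. 10.4.2 itself puts the part 2 PFS and OS tests in the FAS, and alpha, power and event counts are untouched.
- **A randomised DCR comparison would be distorted.** The plan defines DCR but states no between-arm method. DoR covers responders only, so early stoppers without a response never enter it.
- **The EPP would inflate the benefit of TG4001.** The counts in the sensitivity table are assumptions, and the shift can go either way. The 32 patients included in part 1 (Section 1.3.6) against 28 evaluable at the cut-off (Section 1.3.7) is a gap of 4/32 = 12.5%. It comes from a single arm, may include patients not yet scanned, and says nothing about imbalance.
- **The control-arm EPP will in fact shrink to early progressors.** That is the literal text. Whether the data review would apply it that way cannot be told.

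The direction and size of any bias therefore cannot be derived from the documents. The correction is worth making before the final analysis because it is short and follows the plan's own rule.

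**What to change.** 1. Limit the opening sentence of Section 10.4.2 to phase Ib and phase II part 1.
2. Add: *Phase II part 2: all efficacy endpoints, including ORR and DCR, are analysed on the FAS and repeated on the EPP; FAS patients with no evaluable post-baseline assessment count as non-responders and as not having disease control.*
3. State in Section 8 that the week-6 scan condition defines the EPP only.

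The EPP stays as the repeat, so its TG4001 exposure minimum also needs wording that can apply to the avelumab-alone arm. That is a separate edit to Section 10.1.

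The cost is a few sentences. Section 10.3.1 already calls for FAS and EPP analyses in part 2, and no new data are needed. Part 2 response rates may read slightly lower, because patients without an assessment stay in the denominator.

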- For the cohort of patients without liver metastases at baseline, an adaptive sample size re-estimation is applied: based on the results obtained in phase II part 1, the hypothesis for median PFS in the combination arm (TG4001 with avelumab) is set at 4.5 months. The hypothesis for median PFS in the monotreatment arm (avelumab alone) is set at 2 months. The type I error α is set at 5% one sided, the type II error β is set at 5%.

A two-stage group sequential design will be used with logrank test and boundary for efficacy at $\alpha=0.00001$ and Conditional Power (CP) at 10% for futility.

At the interim analysis, a first test for efficacy is performed on 37 PFS events at a level of significance of 0.000001. A sample size of 50 patients is estimated at time of the Interim Analysis.

Otherwise, the following decision rules are applied based on CP using CHW (Cui, Hung and Wang) approach.

- Favorable zone: If the interim results are sufficiently favorable corresponding to a CP of more than 90%, final analysis will be performed on 74 PFS events corresponding to an estimated sample size of 80 patients.
- Promising zone: If the interim results are equivalent to a CP between 90% and 30%, the sample size will be recalculated according to the median PFS observed in the two arms with a cap of 2 times the initial number of events.

- Unfavorable zone: If the interim results are not favorable corresponding to a CP between 30% and 10%, the trial may continue up to the initial sample size of 80 patients or could be stopped.
- Futility zone: If the interim results are futile corresponding to a CP lower than 10%, the trial will be stopped for futility at the interim analysis.

[figure not shown]
Assuming uniform enrollment with 3 patients per month, an average of 136 patients are needed to observe 124 PFS events. Assuming a 5% lost to follow-up or withdrawal of consent rate, a total of 142 patients should be randomized to the 2 treatment arms in a 1:1 ratio (71 patients in each treatment arm).

[REDACTED]

[REDACTED]

[REDACTED]

[REDACTED]

- For the cohort of patients with liver metastases at baseline, [REDACTED]

[REDACTED]

[REDACTED]

[REDACTED]

[REDACTED]

TABLE OF CONTENTS

INVESTIGATORS / STUDY ADMINISTRATIVE STRUCTURE.....	2
DOCUMENT APPROVAL.....	3
SYNOPSIS.....	4
TABLE OF CONTENTS.....	17
ABBREVIATIONS / DEFINITION OF TERMS	21
1 INTRODUCTION.....	26
1.1. BACKGROUND AND INTRODUCTION	26
1.1.1. Human PapillomaVirus (HPV) and related diseases	26

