The phase II part 2 of the study is designed as a randomized, open label, controlled two arms study comparing the PFS of TG4001 in combination with avelumab vs avelumab alone. For the cohort of patients without liver metastases at baseline, due to the uncertainty on the true treatment effect and data variability, and to reduce the risk of running an underpowered study, it is considered appropriate to adopt an adaptive approach to the sample. This will offer a mechanism to adjust the sample size to updated treatment effect and variability estimates seen at a planned interim analysis (Mehta C.R. and Pocock S.J., 2011).

The hypothesis for median PFS in the combination arm (TG4001 with avelumab) is set at 4.5 months and the hypothesis for median PFS in the monotreatment arm (avelumab alone) is set at 2.0 months. Interim analysis is performed after 37 PFS events and based on the conditional power observed, 120 patients should be enrolled to reach at Final Analysis a conditional power of 90% based on 104 PFS. To stick with initial timelines and with an observed enrollment of only 2 patients per month, Final Analysis will be performed based on at least 69 PFS events reaching a conditional power higher than 75% corresponding to at least 80 randomized patients.

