With an one-sided type I error α at 5%, 76 events are needed to reach a power of 95%. This should happen after around 80 patients enrolled (40 patients per arm). Assuming 5% drop-out in each arm, 84 patients will be randomized.

[figure not shown]
Due to the uncertainty on the true treatment effect and data variability, and to reduce the risk of running an underpowered study, it is considered appropriate to adopt an adaptive approach for the sample size. This will offer a mechanism to adjust the sample size in response to treatment effect and variability estimates seen at a planned interim analysis.

The interim analysis will be conducted after 37 events which will occur approximately 16 months after the inclusion of the first patient. At that time, it is estimated to have around 50 patients enrolled. Based on the results of the interim analysis, sample size re-estimation will be performed. According to simulations on CHW (Cui, Hung and Wand) approach using EAST 6.5., the proposal is as follows:

- Start with a fixed sample size calculation based on the primary endpoint.
- Based on the interim analysis result maintain or increase the sample size in order to obtain the desired power of 90%.

Conditional power will be calculated based on the interim results. Should the conditional power be in the favorable or unfavorable range the sample size and the number of events will not be adjusted and will remain at the initial sample size. Conditional power falling into the promising zone will have a sample and events increase. The regions and their implications on sample size are detailed below:

- **Favorable:** If the interim results are sufficiently favorable corresponding to a CP of more than 90%, final analysis will be performed on 74 PFS events corresponding to an estimated sample size of 80 evaluable patients. This will occur approximately 26 months after the inclusion of the first patient.
- **Promising zone:** If the interim results are equivalent to a CP between 90% and 30%, the sample size will be recalculated according to the median PFS observed in the two arms with a cap of 2 times the initial events.
- **Unfavorable zone:** If the interim results are not favorable corresponding to a CP between 30% and 10%, the trial may continue up to the initial sample size of 80 patients or could be stopped
- **Futility:** If the interim results are futile corresponding to a CP lower than 10%, the trial will be stopped for futility at the interim analysis.

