Assuming an uniform enrollment with 3 patients per month and based on simulations, in case of sample size reassessment, an average of 124 events would be needed (corresponding to 136 patients). Assuming a 5% lost to follow-up or withdrawal of consent rate, a total of 142 patients should be randomized to the 2 treatment arms in a 1:1 ratio (71 patients in each treatment arm). Based on the aforementioned assumptions, a power of 70% is expected using an unstratified log-rank test at a 1-sided cumulative 5% level of significance. [REDACTED]

[REDACTED]

[REDACTED]

[REDACTED]

[REDACTED]

Full details of the adaptive method for sample size specified above will be given in the Statistical Analysis Plan (SAP).

Patients with liver metastases at baseline:

A sample size of [REDACTED] is planned.

[REDACTED]

[REDACTED]

[REDACTED]

[REDACTED]

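### The primary PFS test in Section 10.4.2 carries no legible CHW stage weights, although the final event number was reset after the comparative interim to at least 69, below the planned 74

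*Combined protocol and SAP*

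**What the plan says.** **Final test.** Section 10.4.2 makes the primary PFS comparison "using an unstratified log rank test at the one-sided 5% level in the FAS". A stratified log-rank is supportive, and hazard ratios come from stratified and unstratified Cox models. Section 10.2 names the same kind of test for the re-estimated design: "using an unstratified log-rank test at a 1-sided cumulative 5% level of significance". Neither section legibly mentions stage weights.

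**Adaptation.** The synopsis, in its sample-size text for Phase II part 2, says: "Otherwise, the following decision rules are applied based on CP using CHW (Cui, Hung and Wang) approach". Section 10.2 introduces its proposal with "According to simulations on CHW (Cui, Hung and Wand) approach using EAST 6.5". Under the written zones the number of events stays at the initial plan in the favorable and unfavorable zones. It rises in the promising zone, to at most twice the initial number, and conditional power below 10% stops the trial. The planned final number is 74 events, with the interim at 37.

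**What happened after the interim.** Section 3.2 reports that 104 events would give 90% conditional power. It then says, citing timelines and accrual of 2 patients per month: "Final Analysis will be performed based on at least 69 PFS events reaching a conditional power higher than 75" per cent. Section 3.1.3 has the IDMC evaluate efficacy results at the interim.

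**The concern.** CHW controls type I error by fixing the weights of the two stages before the interim. The final statistic then keeps its null distribution however the second stage is resized. A log-rank on all pooled events instead weights each stage by the events it happens to contribute, so its level can depend on how the final number was chosen once the interim result was known.

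While events are only held or increased under the written promising-zone rule, the unweighted test is slightly conservative. Section 3.2 leaves that rule: the new number is below 74, is open-ended, and was set when the interim conditional power was known. The legible primary-test sentence does not say whether the CHW weights apply. The error control of the primary endpoint therefore rests on an unstated choice, and that choice would not be credible if made after the final data are seen.

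**Working it through.** **Inputs.** Interim at 37 events and planned final at 74 (synopsis, Section 10.2); one-sided 5%, critical value 1.645 (the interim efficacy level is too small to change it); medians 4.5 and 2.0 months; 90% conditional power at 104 events, and more than 75% at 69 or more (Section 3.2). The interim z is not disclosed.

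**Plan's own event number.** HR = 2/4.5 = 0.444. Freedman's formula gives [(1 + 0.444)/(1 − 0.444)]² × (1.645 + 1.645)² = 6.76 × 10.82 = 73.2, so 74 events. This matches the planned 74. Section 10.2 also prints a slightly larger number: "With an one-sided type I error α at 5%, 76 events are needed to reach a power of 95" per cent.

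**Statistic.** Z = sqrt(w)·z1 + sqrt(1 − w)·z2, where z1 is the log-rank z at 37 events and z2 comes from the increment after it. CHW fixes w = 37/74 = 0.5. The unweighted log-rank at D events has w = 37/D, which is 0.536 at 69 and 0.356 at 104.

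**Conditional type I error.** Φ[(sqrt(w)·z1 − 1.645)/sqrt(1 − w)]. At z1 = 1.538 (derived below):

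| Final test | Argument | Conditional error |
|---|---|---|
| Original plan (74 events), or CHW at any D | −0.788 | 21.5% |
| Unweighted, 104 events | −0.906 | 18.2% |
| Unweighted, 69 events | −0.762 | 22.3% |

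Increasing the events is conservative here; cutting below 74 exceeds what the plan allowed.

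**Overall one-sided error.** The conditional error was integrated over z1 ~ N(0,1), with zones set by observed-trend conditional power and no credit for the futility stop:

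| Rule for final events | Unweighted | CHW |
|---|---|---|
| 74 always | 5.00% | 5.00% |
| Written increase-only rule, cap 148 | 4.73% | 5.00% |
| Promising zone to 69, otherwise 74 | 5.04% | 5.00% |
| Worst choice from 69 to 104 after any z1 | 5.75% | 5.00% |

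If the futility stop is always obeyed and credited, the third row becomes 4.51% and 4.47%.

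**Conditional power at 69 events.** Under the observed trend, CP(D) = Φ[(sqrt(w)·z1 − 1.645)/sqrt(1 − w) + z1·sqrt((D − 37)/37)]. Solve CP(104) = 90% for z1, then set D = 69.

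- CHW: z1 = 1.538. At 104: −0.788 + 2.070 = 1.281, 90%. At 69: −0.788 + 1.430 = 0.642, **74.0%**.
- Unweighted: z1 = 1.595. At 104: −0.864 + 2.146 = 1.282, 90%. At 69: −0.701 + 1.483 = 0.782, **78.3%**.

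CHW gives 75.4% at 71 events, and passes 75% at 69 events if the 90% was really about 90.7%. Weights based on 76 planned events give 73.9%.

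**The case against.** **A reader might infer that the plan names two different final tests.** It does not. Only one final test is named, and CHW is attached to the decision rules and the re-estimation simulations. A CHW statistic is itself built from unstratified log-rank increments, so the test sentences are silent on weights rather than contradictory. Text is redacted after the test sentence in Section 10.2, and after the supportive-test sentence in Section 10.4.2. Section 10.2 also defers the full adaptive method to the SAP. The weights may be stated there. This stands, and it limits the point to the legible text.

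**A reader might infer different critical values.** Both statistics are compared with about 1.645 and differ only in the stage weights. At 69 events their null correlation is sqrt(0.5 × 0.536) + sqrt(0.5 × 0.464) = 0.999.

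**A reader might infer that the printed conditional power fits only the unweighted test.** The CHW shortfall is one point, from a back-solved z and a rounded 90%, and Section 3.2 says at least 69. Re-estimation uses the observed medians, so the assumed effect need not equal the interim log-rank trend. For illustration, an assumed z1 of 1.70 with an HR near 0.63 gives CHW about 90% at 104 events and 75.6% at 69. The printed figure cannot identify the test.

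**The inflation is negligible, and the stated reason is accrual.** The size is indeed small. A change truly independent of the interim result would not inflate the error at all. But Section 3.2 sets the number with the interim conditional power in hand and cites it in support, so independence cannot be assumed.

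**Conclusion.** The point holds as a should-fix clarification of the primary analysis. The legible test has no stage weights, the design invokes CHW, and the event number was reset after a comparative interim to a value below plan and outside the pre-set rule. The unweighted log-rank then no longer guarantees 5%: about 5.04% on the 69-event path, and at most about 5.8% under free choice from 69 to 104 events. CHW holds 5.0% in each case.

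These figures assume 74 planned events, zones set by observed-trend conditional power, and futility treated as non-binding. With futility binding, the 69-event path stays below 5% for both tests, with the unweighted test still marginally above CHW.

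The values of about 74% (CHW) and 78% (unweighted) at 69 events are indicative only. They do not show that the stated conditional power is wrong, and neither is a figure to print.

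**What to change.** In Sections 10.4.2 and 10.2, define the primary PFS statistic as sqrt(37/74) times the stage-1 log-rank z plus sqrt(37/74) times the z from the log-rank increment after the interim, tested against the one-sided 5% critical value (about 1.645). Keep the pooled log-rank and the Cox hazard ratio as supportive. If the redacted text or the SAP already says this, a cross-reference in both sections is enough.

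The sponsor should recompute the conditional power at the final event number from the actual interim result with this statistic, say which statistic it refers to, and restate it in Section 3.2 if it is not above 75%.

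The cost is one paragraph and one recalculation, with no extra data. The stated conditional power may become slightly less favourable. The change should be made before the final analysis.
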